3.3.2. RANDOMIZATION

Not applicable. This is a FU study for subjects who completed Study ALX0681-C301. Upon a recurrence of TTP, subjects will receive open-label treatment with caplacizumab in addition to standard of care.

After obtaining oral and written informed consent, subjects will be screened according to the inclusion and exclusion criteria and will receive a unique subject identification (ID) number.

3.3.3. IDENTITY OF STUDY DRUG

The study medication is provided in a kit containing the following components:

- One glass vial containing lyophilized powder (caplacizumab) for reconstitution.
- One prefilled glass syringe containing solvent for reconstitution (containing WFI).
- One "vial adapter" device to facilitate transfer of the solvent for reconstitution and subsequent recovery of the reconstituted drug.
- One safety needle for s.c. use (please note that a needle for the first i.v. bolus injection is not included in the kit).
- Two alcohol pads.

Further details on drug components:

- Caplacizumab 10 mg – lyophilized powder for solution for injection
 - Presented in ISO 2R glass vial with FluroTec® Butyl stopper filled with lyophilisate containing 12.5 mg caplacizumab and excipients (see below).
 - Active substance: caplacizumab (anti-vWF Nanobody).
 - Activity: caplacizumab is directed towards the A1 domain of vWF and specifically inhibits the interaction of (UL)vWF with the platelet GPIb receptor glycoprotein, thereby preventing (UL)vWF-mediated platelet aggregation.
 - Strength: One vial contains 12.5 mg of caplacizumab and comprises an overfill to compensate for losses during reconstitution and liquid transfer. After reconstitution using the supplied kit components, the resulting solution contains 11.1 mg/mL of caplacizumab (the total volume of the reconstituted solution is slightly more than 1 mL because the lyophilisate also takes up a certain volume). Taking into account losses, e.g., during transfer from vial to syringe, the nominal administered dose is 10 mg when injecting the entire contents (nominally 0.9 mL) of the syringe.
 - Excipients: 0.21 mg citric acid, 5.58 mg tri-sodium citrate di-hydrate, 70 mg sucrose, 0.11 mg polysorbate-80 per vial (pH 6.5 +/- 0.5).
 - Dosage form: powder for solution for injection; reconstitution with WFI yields solution for injection.
 - Route of administration: i.v. (first dose), s.c. (all subsequent doses).

3.3.4. DRUG ACCOUNTABILITY

The Pharmacist or his/her designee is responsible for acknowledging receipt of each shipment of study drug and will verify the condition and quantity of the study drug.

At study site, the study drug will be kept in a locked and secured storage facility accessible only to those authorized by the Investigator to dispense the study drug.

The responsible person will keep an inventory. This will include the quantity of study drug received for the study and a record of the materials that are dispensed, to whom (subject number) and when.

At all ambulatory study drug administrations, the subject will note information with regard to the study drug administration (e.g., the timing, kit number, injection location, who performed the injection) in the patient diary. All used and unused vials and syringes should be returned to the site at the following clinic visit. These should not be used for future administrations (including administrations at the study site). The subject must bring his/her patient diary to all recurrence visits. At each recurrence visit, site personnel will review the patient diary. At each visit, site personnel will record the new information in the electronic case report form (eCRF) (also see section 3.3.6), and return the diary to the subject. Subjects will be instructed to return the completed diary at the latest at the recurrence FU visit.

The pharmacist, the Investigator and/or designated personnel will conduct a final inventory of the study drug supply and will record the results of this inventory in the Drug Accountability Form. Upon Sponsor approval, all study drug supplies will be returned to the depot, or will be locally destroyed according to local regulations and site procedures.

Instructions for drug accountability are available in the manual concerning study drug.

3.3.5. STUDY DRUG HANDLING

Instructions for study drug receipt, handling, storage and administration are available in the manual concerning study drug.

Packaging and Labeling

The study drug will be labeled with at least study number, storage conditions, dosing instructions, Sponsor's name, address and telephone number in accordance with Annex 13 of EudraLex Volume 4 requirements and local regulations.

One IMP kit contains 1 vial of caplacizumab, 1 syringe with water for injection, 1 vial adapter, 1 safety needle for s.c. injection and 2 alcohol pads. Note that a needle for the first i.v. bolus injection is not included in the kit and an appropriate i.v. needle available at the site should be used.

Storage

The IMP kit will be provided under refrigerated conditions and must be stored in a secure, limited-access location under the storage conditions specified by the Sponsor.

The IMP kit must be refrigerated at 2°C to 8°C (35.6 °F to 46.4 °F) and should be stored in the secondary packaging until administration. It should not be frozen or shaken.

Site storage conditions should be monitored by the site personnel and reviewed by the monitor during site visits. Deviations from the storage requirements must be documented and reported to the Sponsor, according to the instructions provided in the manual concerning study drug.

Verbal and written instructions for proper storage, handling, and administration of the study drug will be given to the subject, and will include instructions to contact the study site immediately if they experience problems with the study drug and/or its administration.

Dispensing

The Investigator or qualified designee(s) will dispense study drug to subjects who have met the entry and caplacizumab treatment criteria. Clinical supplies may not be used for any purpose other than that which is stated in this protocol.

For ambulatory study drug administrations, enough IMP until the next visit will be provided for the subjects to take home. Note: On days a visit to the study site is planned, subjects should not self-administer study drug prior to their visit. Study drug administration will be done after all visit assessments have been performed.

Product Quality Complaint

Any malfunction has to be communicated by completion of the Sponsor's IMP Notification Form and the malfunctioning IMP kit has to be returned to the Sponsor or its designee upon Sponsor's request.

3.3.6. STUDY DRUG ADMINISTRATION

Detailed instructions for study drug administration are available in the manual concerning study drug.

Daily PE period

- Loading i.v. dose: subjects will receive a single loading dose of 10 mg study drug by i.v. bolus injection from 6 hours to 15 minutes prior to PE (i.e., prior to the first session in case PE is given over multiple sessions within 24 hours) by a health professional. Of note, up to 1 PE (which may be spread over 2 or more sessions in 24 hours) may be given prior to initiation of treatment with caplacizumab as long as considered part of the PE for the treatment of the presenting TTP episode.
- Daily s.c. dose: From caplacizumab treatment Day 1 and throughout the daily PE period, study drug is to be administered daily s.c. within 2 hours after end of PE (i.e., after the last session in case PE is given over multiple sessions within 24 hours). In case of

tapering, study drug should be administered as specified above on days PE is done and at approximately the same time as on the day before on days when there is no PE.

It is expected that subjects are hospitalized for the duration of the daily PE period. At the clinical site, subjects will be observed in order to assess adverse reactions (e.g., hypersensitivity reactions).

30-day post-daily PE period

After subjects are discharged from hospital, subjects should self-administer study drug (training will be given during hospitalization on how to prepare and s.c. inject the study drug). Subjects will be instructed to administer study drug at approximately the same time during the day and will be requested to be accompanied by a second person during administration and for a period of 30 minutes afterwards. In case the subject is unable or unwilling to self-administer, study drug may be administered by a caregiver who has been trained at the site.

For all study drug injections, study drug administrations should occur approximately 24 hours apart with a minimum of 12 hours apart.

Note: On days a visit to the study site is planned, subjects should not self-administer study drug prior to their visit. Study drug administration will be done after all visit assessments have been performed.

Subcutaneous injections are to be performed in the abdominal region. As injections are to be performed daily, injections need to be performed in a different quadrant than the quadrant in which study drug was injected the previous days. Also note that the area of administration needs to be evaluable for local skin reaction. The location used for the administrations will be noted as a guide/memory aid for the site and for the subject for appropriate rotation of next dose administration.

In case of an injection site reaction, it should be followed-up and documented in which exact quadrant the skin reaction appears.

Information with regard to study drug administration to be recorded in the eCRF will include: time of administration, kit number, route of administration, who performed the administration.

Of note, subjects will be provided with an "In case of emergency card", which will contain at least following information: study number, indication of study drug as "anti-vWF agent", Investigator name and Investigator/site emergency contact details.

Missed Doses

For missed doses during hospitalization, study drug should be administered as soon as possible after the protocol-defined time window and separated by at least 12 hours of the next administration. If the next administration is due within the next 12 hours, then the missed dose should not be given. The next administration should be given at the usual time.

If a subject misses an ambulatory dose, a new injection should be performed as soon as the subject remembers during that day and separated by at least 12 hours of the next administration. If the next administration is due within the next 12 hours, then the missed dose should not be given. The next administration should be given at the usual time.

Management of Overdose

As unbound caplacizumab is assumed to be rapidly cleared by the kidney due to its relatively small size (28 kDa), the risk of overdose is considered (partially) self-limiting.

In case of overdose, there is a potential for increased risk of bleeding based on the pharmacological action of study drug. Subjects should be monitored closely for signs and symptoms of clinically relevant bleeding in case of actual or suspected overdose. In case of clinically relevant bleeding associated with (suspected) overdose, appropriate treatment for bleeding according to standard practice should be initiated and treatment with study drug must be interrupted (also see section 3.2.4). In addition, plasma levels of FVIII:C may be determined locally to assess possible need for treatment with FVIII or FVIII/vWF concentrates. Treatment with study drug should only be restarted when the bleeding has stopped. The PE treatment, if applicable, should continue as clinically indicated.

In case of (suspected) overdose with no clinically relevant bleeding observed, study drug administration may continue after the next PE or next daily dose as applicable.

Note that permanent discontinuation of study drug should be considered for subjects who develop a severe bleeding requiring urgent medical and/or surgical intervention which is accompanied by significantly low FVIII:C levels which are slow to respond to study drug interruption and replacement therapy (also see section 3.2.4). Subjects who have to discontinue study drug but who have not been permanently discontinued from the study, should proceed with the Q6M visits and/or the recurrence visit schedule as originally planned to perform the assessments as specified in the [Schedules of Assessments](#).

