^a Pregnancy test (urine or blood) for female subjects of childbearing potential will be assessed per local laboratory.

^b TTP recurrence information includes presenting symptoms (assessed at recurrence visit), duration (assessed at the Week 1 visit) and outcome (assessed at the recurrence FU visit).

^c Heart rate and blood pressure to be assessed after 5 min in supine position.

^d To be assessed at the post-daily PE Day 29 only.

** Treatment with caplacizumab may not be initiated for subjects who do not fulfil the caplacizumab treatment criteria. These subjects will be treated with standard of care only. For the Schedule of Assessments, please refer to [Appendix 1](#).

-
- ^e Clinical laboratory analyses include hematology (Hb, Hct, RBC, WBC, platelets); chemistry (AST, ALT, LDH, creatinine, protein, cholesterol and CRP). Urinalysis includes assessment of albumin. The results of assessment of platelet count and LDH levels performed as per standard of care (by a local laboratory) at any time during the recurrence period will be collected in the eCRF, if available.
- ^f At the recurrence visit and the Treatment Day 3 visit, samples need to be collected prior to start of the PE treatment and/or study drug administration (whatever comes first). At all subsequent visits, blood samples need to be taken prior to study drug administration.
- ^g In case of a severe and/or serious hypersensitivity reaction, an additional blood sample to characterize the reaction should be collected as soon as possible after the start of the event.
- ^h PD parameters include RICO and vWF:Ag.

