1.1.1. TREATMENT OF ACQUIRED TTP

Plasma exchange (PE) is the current standard of care for treatment of acquired TTP. PE replenishes ADAMTS13, partially normalizing vWF processing, and removes pathogenic autoantibodies. Daily exchanges are to continue for a minimum of 2 days after the platelet count has normalized [12]. Immunosuppression, most commonly in the form of corticosteroids is often started together with PE to reduce the production of autoantibodies. Despite standard of care treatment, an exacerbation occurs in approximately 30% of patients within 30 days of stopping PE [13]. Severe ADAMTS13 deficiency (<10%) has been identified as a potential biomarker of active underlying disease and an elevated risk of relapse in these patients [14, 15].

In spite of recent advances in understanding the disease, there are no approved pharmacologic therapies for acquired TTP. Caplacizumab represents a novel approach to treating the microthrombotic component of acquired TTP. Caplacizumab is being developed with the aim of preventing platelet consumption and formation of further microthrombi thereby reducing the duration of tissue ischemia and protecting the patient from the manifestations of the disease while the underlying process resolves. When used in conjunction with PE for initial and recurrent episodes of acquired TTP, its ability to prevent further microthrombus formation may translate into better long term outcomes for these patients.

[figure not shown]

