Treatment with caplacizumab beyond these 30 days will be guided by a number of risk factors for relapse of the presenting TTP episode and may be accompanied by an optimization of the immunosuppressive treatment. Caplacizumab should be extended for additional 7-day periods up to a maximum of 28 days for subjects who in the opinion of the Investigator have persistent active underlying disease. In parallel, optimization of the immunosuppressive treatment may be considered and includes reversal of corticosteroid tapering through increase or re-initiation of corticosteroid treatment, or start/continuation of other immunosuppressive treatment such as rituximab (as per standard site practice).

Decision on treatment extension

The decision to extend treatment with additional 7-day periods should be made by the Investigator based on the ADAMTS13 activity profile, as well as other signs and symptoms of continued underlying disease activity, such as presence of inhibitors if measured as routine practice by the site.

ADAMTS13 activity will be measured weekly and results of these analyses will be communicated to the clinical sites upon availability.

Caplacizumab treatment should be stopped when ADAMTS13 activity shows a sustained upward trend of >10% or is stable and there are no other signs and symptoms of disease activity, and at the latest on Day 28 of the study drug treatment extension period.

Recurrences during the Recurrence Period

In case of recurrent thrombocytopenia requiring re-initiation of daily PE during an ongoing recurrence period (see [Figure 4](#) and [Table 2](#)), a new visit cycle is to be started, with a recurrence visit on the day of the new recurrence followed by all subsequent visits as indicated in [Table 2](#). All remaining visits of the original schedule are no longer applicable and are not to be performed.

Note: an i.v. loading dose of caplacizumab needs to be administered prior to re-initiation of PE for the recurrence.

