3.4.1.3. RECURRENCE PERIOD

Upon recurrence of TTP, defined as recurrent thrombocytopenia requiring initiation of daily PE, standard of care treatment consisting of daily PE and immunosuppression is to be initiated. In addition, open-label caplacizumab will be administered daily for the duration of daily PE and for 30 days thereafter. Treatment with caplacizumab may be extended for a maximum of 4 weeks in case of persistent signs and symptoms of underlying disease activity (e.g., ADAMTS13 activity profile remains below 10% based on weekly measurements).

The visit schedule upon initiation of treatment consists of a recurrence visit at presentation, a visit on Day 3 of treatment with caplacizumab, weekly visits during treatment with caplacizumab (starting 1 day after the last daily PE), and a recurrence FU visit 1 week after the end of treatment with caplacizumab. Q6M visits that are scheduled within a recurrence period will not be held as assessments at such visits would be confounded by the concurrent recurrence.

In case of recurrent thrombocytopenia requiring re-initiation of daily PE during an ongoing recurrence period (see [Figure 4](#) and [Table 2](#)), a new visit cycle is to be started, with a recurrence visit on the day of the new recurrence followed by all subsequent visits as indicated in [Table 2](#). All remaining visits of the original schedule are no longer applicable and are not to be performed.

If the new recurrence visit coincides with a visit of the original recurrence visit schedule, then assessments already performed for the original recurrence visit do not need to be repeated for the new recurrence visit.

Assessments will include (also see [Schedules of Assessments](#)):

- Review of caplacizumab treatment criteria (at the recurrence visit only)
- Pregnancy test (blood or urine) for female subjects of childbearing potential (Note: pregnancy is an exclusion criterion for treatment with caplacizumab)
- TTP recurrence information (at the recurrence visit, the Week 1 visit and the recurrence FU visit only)
- Concomitant medication
- PE information (at the Week 1 visit only)
- Study drug administration
- Quality of life assessment: SF36 questionnaire (at the recurrence FU visit only)
- Adverse events

- Clinical laboratory analyses include hematology (Hb, Hct, RBC, WBC, platelets) and chemistry (AST, ALT, LDH, creatinine, protein, cholesterol and CRP). Urinalysis includes assessment of albumin.
- Physical examination, vital signs

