3.4.11. APPROPRIATENESS AND TIMING OF MEASUREMENTS

The assessments which will be made in this study are standard and generally recognized as reliable, accurate, and relevant.

The timing of all assessments is detailed in the [Schedules of Assessments](#).

Note that blood samples for ADA, PD parameters and disease-related markers need to be collected prior to start of the PE treatment and/or study drug administration (whatever comes first; at the recurrence visit and the Treatment Day 3 visit) or prior to study drug administration (at all subsequent recurrence visits).

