- The number and percentage of subjects classified as pre-Ab negative, pre-Ab positive, drug-induced TE negative and drug-induced TE positive

NAb assay result

The number and percentage of subjects will be summarized using following categorization. This analysis will be performed on subset of the population, consisting of subjects who were classified as ADA positive based on ADA data.

- Each NAb subject category
- Classified as pre-dose negative, pre-dose positive, TE negative and TE positive

Alternative NAb (null variant) assay result

The number and percentage of subjects will be summarized using following categorization.

- Each alternative NAb subject category
- Classified as pre-dose negative, pre-dose positive, TE negative and TE positive

Incidence of positive alternative NAb samples by visit.

Spaghetti plot of alternative NAb log₁₀ (titer) vs. time. Negative values for alternative NAb (reported as log₁₀ (titer) < 1.98) will be visualized on the graphs as 1.80 (arbitrarily chosen) to allow plotting. The MRD (or sensitivity of the assay) will be visualized as horizontal line at log₁₀ (titer) = 1.98.

Individual line plots of ADA log₁₀ (titer), mADA log₁₀ (titer), NAb log₁₀ (titer), alternative NAb log₁₀ (titer), PK, RICO activity, vWF:Ag concentration, over time with indication of PE treatment days and treatment with rituximab. PE and rituximab treatment days should be visualized on the plot. For ADA, mADA, and alternative NAb titer plotting, negative values (reported as log₁₀ (titer) < 1.98) will be visualized on the graphs as 1.80 (arbitrarily chosen) to allow plotting. The MRD (or sensitivity of the assay) will be visualized as horizontal line at log₁₀ (titer) = 1.98. Negative values for NAb assay (reported as log₁₀ (titer) < 0.36) will be visualized on the graphs as 0.20. The MRD of the NAb assay will be visualized as a horizontal line at log₁₀ (titer) = 0.36. Different responses can be plotted against separate Y-axes above each other, but scale of time-axis should be identical for each plotted response.

Listing of all immunogenicity parameters (ADA log₁₀ (titer), mADA log₁₀(titer), NAb result log₁₀(titer), alternative NAb result log₁₀(titer)) at each time point.

Listing of subject classification based on ADA assay, mADA assay, overall subject classification (based on ADA and mADA assay results) and listing of subject classification based on NAb assay and alternative NAb assay.

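### In treated recurrences, a weekly sample may be drawn after a same-day taper plasma exchange and could not be identified afterwards, so donor ADAMTS13 can read as recovery

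*Protocol*

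**What the plan says.** Protocol sections 3.1.1 and 3.3.1 and SAP section 1.4 count the 30-day post-daily PE period from the stop of daily PE and do not adjust it for tapering. Section 3.3.6 gives the dosing order for that phase: when PE is tapered, "study drug should be administered as specified above on days PE is done", which places the injection within 2 hours after the exchange.

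The sampling rule has two parts. At the recurrence and Day 3 visits, samples must precede PE or study drug, whichever comes first. After that, Table 2 footnote f (repeated in SAP Table 5) says "At all subsequent visits, blood samples need to be taken prior to study drug administration", and section 3.4.11 likewise says "prior to study drug administration (at all subsequent recurrence visits". Neither mentions PE for these later visits.

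On data capture, section 3.4.1.3 lists "PE information (at the Week 1 visit only", and Table 2 agrees. That visit takes place one day after the last daily PE.

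The protocol states why PE matters for these measurements: "PE replenishes ADAMTS13, partially normalizing vWF processing, and removes pathogenic autoantibodies" (section 1.1.1). On their use, section 3.3.1 says "ADAMTS13 activity will be measured weekly and results of these analyses will be communicated to the clinical sites upon availability", and the ADAMTS13 profile is one input to the decision to extend treatment. SAP section 2.1.4.3 also derives the time to sustained ADAMTS13 of at least 10% from two consecutive visits, dated at the first.

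**The concern.** The protocol recognised the hazard early in the episode and guarded against it at the first two visits. The guard then lapses for the phase in which taper sessions can occur. On a taper day that is also a visit day, the order PE, then sample, then drug satisfies every written rule. The sample would then describe partly donor plasma.

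The values at stake are the weekly ADAMTS13 profile, the time to sustained ADAMTS13 of at least 10%, the drug concentrations, RICO and vWF:Ag, and antibody titres that PE can dilute. The SAP has no flag, exclusion or sensitivity analysis for samples drawn after PE. Its listing of sampling times (section 2.4.6.1) is relative to study drug, not to PE.

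**Working it through.** The plan gives no figure to reproduce. The first two steps compare provisions; the last three show scale under stated assumptions.

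**1. Order of events on a taper visit day.** Section 3.3.6 puts PE before drug. Footnote f and section 3.4.11 put the sample before drug. Section 3.3.6 also has drug given after all visit assessments. All three fix something relative to drug; none orders the sample against PE. Both sample–PE–drug and PE–sample–drug comply.

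**2. Can the two be told apart afterwards?** The Week 1 PE item comes before most or all of a taper. PE is also named under Concomitant Therapy (section 3.3.7), which is recorded until the last visit, but the items specified there include start and end dates and frequency and no clock time. SAP section 2.4.2 lists PE without stating a time variable, and the plots in section 2.4.5.5.5 work at day level: "PE and rituximab treatment days should be visualized on the plot". A PE date may therefore be known, but the same-day order is not.

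**3. Size of the effect on one sample.** Assumptions: single-compartment mixing, donor ADAMTS13 of 100%, true value 5%, and V plasma volumes exchanged.
- Fraction replaced = 1 − exp(−V): 39%, 63% and 78% for V = 0.5, 1.0 and 1.5.
- Value after PE = 5·exp(−V) + 100·(1 − exp(−V)):
  - V = 0.5: 3.0 + 39.3 = 42%
  - V = 1.0: 1.8 + 63.2 = 65%
  - V = 1.5: 1.1 + 77.7 = 79%
- Inhibitor would lower this. The fraction x of donor enzyme that must be neutralised for the sample to read 10% solves 5·exp(−V) + 100·(1 − exp(−V))·(1 − x) = 10, giving x = 0.82, 0.87 and 0.89. Less neutralisation than that leaves the sample above 10%.
- Plausibility of V: the TITAN results in section 1.2.4 give 19923 mL over 5.9 PE days and 28307 mL over 7.9, or 3.4 and 3.6 L per day as ratios of means. With an assumed plasma volume of 2.5 to 3.5 L, V is about 3.4/3.5 = 1.0 to 3.6/2.5 = 1.4. These are daily exchanges; taper volumes are not given.

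**4. How many visits.** Taper length and frequency are not in the documents.
- A taper of 1, 2 or 3 weeks would span about 1, 2 or 3 of the visits on post-daily PE Days 8, 15 and 22.
- With 1 to 3 sessions per week placed independently of visits, each such visit falls on a PE day with probability 1/7 to 3/7 (14% to 43%).
- The expected number of visits on a PE day per tapered episode is then 1 × 1/7 = 0.14 to 3 × 3/7 = 1.3. Fewer would be affected, since some samples would be drawn before PE anyway.

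**5. Effect on the ADAMTS13 endpoint.** The event is dated at the first of two consecutive qualifying visits. If true recovery is first present on Day 15 and persists, one post-PE value of at least 10% on Day 8 moves the event from Day 15 to Day 8, 7 days early.

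**The case against.** Much can be said against a broad reading, and several points stand.

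- A reader might infer that taper PE is never recorded and that the individual plots would show none. The documents do not support that. PE is named under concomitant therapy (Protocol 3.3.7) and as a non-investigational product (SAP 2.1.2), the SAP lists it, and the plots are meant to show PE days. What is missing is PE clock time.
- A reader might extend the point to episodes without caplacizumab. Those have no weekly samples, and Appendix 1 collects PE information 30 days after daily PE, late enough to cover a taper within that period. No defect is shown there.
- A reader might infer that extension decisions would be wrong. Extension arises only after the 30 days, when a short taper is over. It rests on a profile, a sustained trend and other signs, not on one value. In an alternate-day taper starting on Day 2, exchanges fall on even days, so nominal Days 8 and 22 could be affected but not Days 15 and 29; consecutive nominal visits would not both be affected, although the ±1-day window could change this.
- The SAP partly handles antibodies: the modified assay separates drug-induced from pre-existing antibody (2.4.5.5.2), which largely covers transfer from donor plasma. Dilution is not covered.
- Sample handling is delegated to a Lab Manual that is not available here and may say more.

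None of this alters the main point. The written rule permits a post-PE sample, and the specified data do not identify it.

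**Conclusion.** The point holds for caplacizumab-treated recurrences with tapered PE on a visit day. A post-PE draw is permitted, not required. Under the stated mixing assumptions and with no inhibitor, one such sample can lift a true 5% to between 42% and 79%, well past the 10% threshold. Inhibitor would have to neutralise roughly 82% to 89% of the donor enzyme for it not to cross. No figure is offered for drug concentration, because redistribution, continuing absorption and vWF-bound drug make the simple model unreliable there.

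The number of affected samples cannot be derived from the documents, and with short tapers it would be small. The study is descriptive with no formal testing, so no error rate is at stake. What is at stake is the reading of the ADAMTS13 course, a planned time-to-event summary and the accompanying PK, PD and antibody profiles. Correction is worthwhile mainly because it is cheap and extends a rule that the protocol already applies at two visits.

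**What to change.** 1. In Protocol Table 2 footnote f, section 3.4.11 and SAP Table 5, require that on any recurrence visit day with PE, taper PE included, samples are drawn before that PE and before study drug.
2. In section 3.4.1.3 and Table 2, record the date, start and end time and volume of every PE through the recurrence follow-up visit. Dates and volumes alone would not support the flag in item 3. A complete date record also shows carry-over from an earlier day's PE, which pre-PE sampling does not remove.
3. In SAP sections 2.1.4.3 and 2.4.6–2.4.7, flag samples drawn after a same-day PE and repeat the ADAMTS13 (including time to sustained 10% or more), PK and PD summaries without them.

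If sampling is already complete, items 2 and 3 can still be attempted before database lock where site source records hold PE times.

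The cost is repeated use of an existing PE eCRF item and one extra set of summaries. No visit or sample is added.
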